9.2 Setting

Study drug users will be selected from the outpatient pharmacy database. This database records all outpatient dispensings from primary and secondary care in a well-defined geographic area. All study drug users living in this area will be captured in the database. All patients aged 2 years and above who have been registered in the database for at least 1 year before the index date will be included. A sub-population will be defined of patients for whom GP recorded information is also available.

The enrolment period will start on December 10, 2011 (the day after rivaroxaban received first marketing authorization in the Netherlands for the ‘treatment of DVT and long-term secondary prevention of recurrent DVT and PE’). End of enrolment will be 31 December 2017 and end of follow-up will be 31 December 2018. Interim reports will be provided for data collected 2 and 4 years after the date that rivaroxaban receives reimbursement approval for DVT treatment (see [Section 6](#) for detailed milestones). The characteristics of the two study cohorts in the first year and subsequent years of the enrolment period will be compared.

The drug utilization analysis ([Section 8.1.1](#)) will be performed in the sub-population captured by both the outpatient pharmacy database and the GP database, in order to enrich the data for the assignment of indication of use.

The Adverse Outcomes analysis (Sections [8.1.2](#) and [8.2](#)) will be performed in the full rivaroxaban cohort (outpatient pharmacy database with outcomes available from Medical Register), using the dosing as a proxy for the indication when this information is not available, and in the subcohort of comparator drug users captured by both the outpatient pharmacy database and the GP database.

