9.3 Variables

9.3.1 Patient characteristics and drug utilization

Descriptive variables of drug utilization will be presented only for the subpopulation captured by both the outpatient pharmacy database and the GP database, as only in this subpopulation sufficient information for the assignment of the indication of use is available. The following characteristics, including risk factors/potential confounders for the outcomes under study, will be presented for comparison between the two cohorts:

- age and sex distribution at index date 
- dose of index drug at index date (not available for vitamin K antagonists as dosing is determined in anticoagulation clinics) 

- dispensed amount (can be used to estimate duration of treatment) ✓
- where available based on hospital discharge diagnosis or from available GP notes, diagnosis associated with the prescribing of the index drug (where not available, dose and duration of index drug will be used as a proxy for the associated diagnosis among rivaroxaban users). Hospital discharge diagnoses and procedures will be identified within 4 weeks before until 7 days after the index date and GP diagnosed will be identified during the index month or in the month before the index date.
- proportion of patients defined as naïve, non-naïve, recent switchers and distant switchers ✓
- number of pregnant women at index date (if communicated by midwife or gynaecologist) ✓
- number of pregnancies after index date (if communicated by midwife or gynaecologist) ✓
- type of other anticoagulant use before the index date among the non-naïve group ✓
- use of specific prescribed medications both in the year before the index date and following the index date, confirming the ACS indication: antiplatelet drugs (low-dose acetylsalicylic acid, clopidogrel, dipyridamole, prasugrel, ticlopidine and ticagrelor); ✓

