9.3.2.3 Secondary outcomes related to effectiveness

DVT and PE (Annex 3, Table 9)

A patient will have to meet the following criteria to be considered a case of DVT or PE:

- the patient having been admitted to hospital with a diagnosis of DVT or PE
- or
- having a DVT or PE diagnosis documented in the general practitioner database.

Ischaemic stroke (Annex 3, Table 10)

A patient will have to meet the following criteria to be considered a case of ischaemic stroke: the patient having been admitted to hospital with a diagnosis of ischaemic stroke.

MI (Annex 3, Table 11)

A patient will have to meet the following criteria to be considered a case of MI: the patient having been admitted to hospital with a diagnosis of MI.

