9.4 Data sources

Data for the study will be obtained from a linked cohort created using the PHARMO Database Network. The PHARMO Database Network is a population-based network of healthcare databases and combines data from different healthcare settings in the Netherlands. These different data sources are linked on a patient level through validated algorithms. Detailed information on the methodology and the validation of the used record-linkage method can be found elsewhere ([van Herk-Sukel et al. 2010](#); [Herings RMC 2012](#))

The longitudinal nature of the PHARMO Database Network system enables follow-up of more than 4 million residents (25% of total population) of a well-defined population in the Netherlands for an average of ten years. Data collection period, catchment area and overlap between data sources differs. Therefore, the final cohort size for any study will depend on the data sources included. As data sources are linked on an annual basis, the average lag time of the data is 1 year. All electronic patient records in the PHARMO Database Network include information on age, sex, socio-economic status and mortality. Other information available is dependent on the data source

To address the objectives of the present study, the following data sources will be used: outpatient pharmacy database, Dutch National Medical Register, general practitioner (GP) data and inpatient pharmacy database. The outpatient pharmacy database has a source population of about 4 million residents and is fully linked to the national Dutch National Medical Register. The GP and inpatient pharmacy databases each represent different, partially overlapping subsets of the outpatient pharmacy/Medical Register source population.

The drug utilization analysis will be performed in the subpopulation captured by both the outpatient pharmacy database and the GP database, in order to enrich the data for the assignment of indication of use. The Adverse Outcomes analysis will be performed in the full rivaroxaban cohort (outpatient pharmacy database with outcomes available from Medical Register), using the dosing regimen as a proxy for the indication when this information is not available, and in the subcohort of comparator drug users captured by both the outpatient pharmacy database and the GP database.

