9.7.2 Safety and effectiveness outcomes

The two cohorts (of first-time users of rivaroxaban and first-time users of standard of care) will be followed up from the index date until 12 months after the end of the enrolment period for potential outcomes (safety and effectiveness). For each outcome, the first hospitalization for that outcome during the follow-up period will be identified. A separate follow-up will be performed for each of the outcomes.

For all outcomes (for DVT/PE treatment, SPAF and ACS), crude incidence rates will be estimated in both cohorts, using an as-treated approach. In this, person–time will be categorized into current, recent, past and non use. Current use will refer to person–time up to 7 days after the end of supply of the index drug, recent use will refer to person–time up to 90 days after the end of current use, past use will include all person–time contribution after the end of recent use up to 1 year after the end of current use, non-use will include all remaining time person–time contribution after past-use until end of follow-up.

Age- and sex-adjusted rate ratios with 95% CIs will be estimated for each of the three adverse outcomes comparing rivaroxaban with standard of care using Poisson regression analysis. Where numbers and data permit, adjustment will be made for relevant co-medication (described in the drug utilization section), indication and previous hospitalization for bleeding.

As a general strategy, no data imputation strategies will be applied to supplement missing data. The requirement for inclusion is complete data for critical variables such as exposure to rivaroxaban or standard of care and hospitalizations for bleedings or any other outcome event; otherwise this individual is not eligible to be a member of the study population. However, missing values may occur for potential confounder or effect modifying variables. In this case, individuals with missing values will be kept in the analysis and a separate category will be created for missing values of that variable. In sub-analyses to evaluate confounding or effect modification by variables with a large proportion of missing values, the evaluation will be considered to be conducted on the subset with complete data for the variable of interest.

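### The outcome analysis sets the full rivaroxaban cohort against GP-linked comparators only, so DVT/PE capture and the assignment of indication differ by arm

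*Protocol*

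**What the plan says.** Protocol section 9.4 says of the outcome comparison that it "will be performed in the full rivaroxaban cohort (outpatient pharmacy database with outcomes available from Medical Register), using the dosing regimen as a proxy"; the proxy serves to assign an indication where none is recorded. Comparators enter only if they are also in the GP database: "and in the subcohort of comparator drug users captured by both the outpatient pharmacy database and the GP database" (9.2, repeated in 9.4). The GP database covers only a subset of the pharmacy/Medical Register population (9.4).

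On DVT/PE, section 9.3.2.3 accepts a hospital admission or, as an alternative, "having a DVT or PE diagnosis documented in the general practitioner database". Section 9.3.2 says that potential cases of each outcome are identified from hospital discharge codes, and 9.7.2 takes the first hospitalization for each outcome.

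On indication, section 9.3.1 uses discharge diagnoses from 4 weeks before to 7 days after the index date, and for GP data "GP diagnosed will be identified during the index month or in the month before the index date". Where neither exists, dose and duration are the fallback for rivaroxaban users only; dose is not available for vitamin K antagonists. The same section limits the drug utilization description to GP-linked patients, "as only in this subpopulation sufficient information for the assignment of the indication of use is available". Section 9.7.2 estimates rates for DVT/PE treatment, SPAF and ACS, and lists indication among the adjustment variables where numbers and data permit.

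**The concern.** The two arms of one comparison come from different source populations, and GP data do two jobs in it: they can supply DVT/PE events and they supply indication. Both then depend on the arm as well as on the patient.

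For DVT/PE, an effectiveness outcome, unequal capture works in one direction. Rivaroxaban users without GP data cannot have a GP-only event, so their rate is too low relative to comparators.

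For indication, the strata and the adjustment variable do not mean the same thing in both arms. A comparator is placed in a stratum by a diagnosis recorded near the index date. A rivaroxaban user may be placed there by dosing alone. This reaches the primary bleeding outcomes, because their rates are estimated for these indications. The direction of any resulting bias cannot be read from the protocol.

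Neither the limitations (9.9) nor the sensitivity analyses (9.7.2.2) mention the asymmetry, and the protocol plans no outcome analysis with both arms from the same source.

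**Working it through.** **1. Which outcomes depend on GP data**

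| Outcome | Case source in the protocol | Capture depends on GP link? |
|---|---|---|
| Intracranial, gastrointestinal, urogenital bleeding (9.3.2.1) | Hospital discharge | No |
| Other bleeding, liver disease (9.3.2.2) | Hospital discharge | No |
| Ischaemic stroke, MI (9.3.2.3) | Hospital admission | No |
| DVT/PE (9.3.2.3) | Hospital admission or GP record | Yes, if the GP route is used |
| Death (9.3.2.4) | Several databases, confirmed by external linkage | Not shown |

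The pharmacy database is fully linked to the Medical Register (9.4), so hospital events are captured alike in both arms.

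**2. Size of the DVT/PE effect**

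Let s be the share of DVT/PE cases recorded only by the GP and g the GP-linked share of rivaroxaban person-time. Neither is in the protocol; both are assumptions. Take the same true rate λ in both arms and in linked and unlinked patients.

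- Comparators, all GP-linked: observed rate λ.
- Rivaroxaban: hospital-captured part λ(1 − s), plus GP-only part λ·s·g.
- Apparent ratio = (1 − s) + s·g = 1 − s(1 − g).

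At s = 0.3 and g = 0.5: 1 − 0.3 × 0.5 = 0.85.

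| s | g = 0.25 | g = 0.50 | g = 0.75 |
|---|---|---|---|
| 0.1 | 0.925 | 0.950 | 0.975 |
| 0.3 | 0.775 | 0.850 | 0.925 |
| 0.5 | 0.625 | 0.750 | 0.875 |

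The ratio is below 1 whenever s > 0 and g < 1. With hospital records only, s = 0 and the effect disappears.

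**3. Indication**

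- The diagnosis windows in 9.3.1 are the same for both cohorts. The fallback is not: rivaroxaban users without a diagnosis get a dosing-based indication; vitamin K antagonist users cannot.
- Section 9.3.1 says that indication is sufficiently known only in the GP-linked subpopulation, yet 9.2 and 9.4 analyse rivaroxaban users outside it.
- Section 7 lists 20 mg once daily both for SPAF and as a continuation dose in DVT/PE treatment, so that dose alone does not distinguish the two.

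**4. Precision of a GP-linked analysis**

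First the plan's own figure (9.5). At 5 per 1000 person-years, 12,000 and 48,000 person-years give 60 and 240 expected events. SE of the log rate ratio = √(1/60 + 1/240) = 0.1443. Power to exclude 1.5 when the true ratio is 1, with two-sided 0.05 assumed from the 95% CI, is Φ(ln 1.5/0.1443 − 1.96) = 80.2%. The stated 80% reproduces.

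Restricting both arms to GP-linked patients, with the retained share assumed:

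| Share retained | Both arms shrink | Only rivaroxaban shrinks, comparators stay at 48,000 |
|---|---|---|
| 0.75 | 68% | 70% |
| 0.50 | 51% | 55% |
| 0.30 | 34% | 38% |

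At a share of 0.4 with 48,000 comparator person-years, rivaroxaban has 4,800 person-years and 24 events. SE = √(1/24 + 1/240) = 0.2141 and power is about 47%.

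**The case against.** The restriction is deliberate and has a reason. Vitamin K antagonist dose is unavailable, so comparators need recorded diagnoses, and keeping all rivaroxaban users protects the arm whose size depends on market uptake. The calculation in step 4 shows that this has real value. That stands as a reason not to make the GP-linked set the main analysis. It does not justify leaving the asymmetry unexamined and undisclosed.

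DVT/PE is a secondary outcome. Section 9.7.2 specifies rate ratios only for the three adverse outcomes, and the general text in 9.3.2 and 9.7.2 points to hospital records. So GP-only capture is one side of an internal conflict, not a settled rule. That is fair. But 9.3.2.3 is the specific case definition, 9.7.2 reports DVT/PE rates in both cohorts, and section 8 states the aim as a comparison.

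On dosing, the protocol also uses duration (9.3.1, 9.7.1), and section 7 gives DVT/PE treatment a distinct initial phase of 15 mg twice daily. Dosing can therefore separate some patients. It is less informative when treatment began in hospital and outpatient records miss the start, which 9.9 acknowledges can happen.

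Three stronger inferences are tempting and are not supported:

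- *Bleeding events are captured unequally.* They are not: they come from hospital records under full linkage.
- *The missing-value category becomes a marker of rivaroxaban.* Section 9.7.2 does say "individuals with missing values will be kept in the analysis and a separate category will be created for missing values of that variable". But eGFR, BMI and smoking are not in the stated adjustment set, no source is given for BMI and smoking, and 9.7.2 moves sub-analyses of heavily missing variables to patients with complete data.
- *The comparator restriction breaks the 80% power.* The 48,000 person-years are a requirement from a preliminary calculation, not a forecast. Nothing shows that GP-linked comparators fall short of it.

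**Conclusion.** The concern holds for two specific consequences of drawing the arms from different sources.

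- **DVT/PE.** If the case definition in 9.3.2.3 is followed, the crude rates favour rivaroxaban. Under a true ratio of 1 the apparent ratio runs from 0.975 to 0.625 over the assumed grid, with 0.85 at s = 0.3 and g = 0.5. The direction follows from the design; the size rests on s and g, which the protocol does not give. If only hospital records count, this bias is nil, but the sections must then be reconciled.
- **Indication.** It is assigned by different means in the two arms while defining the strata and serving as an adjustment variable. This can affect the primary bleeding comparisons through misclassified strata. Neither its size nor its direction can be derived from the protocol.

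The protocol does not show that the bleeding comparisons are invalid or that the full rivaroxaban cohort must be dropped from the main analysis.

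**What to change.** 1. Reconcile 9.3.2.3 with 9.3.2 and 9.7.2. For any comparison that uses the full rivaroxaban cohort, count DVT/PE from hospital records only, in both arms. Count GP-recorded DVT/PE only where both arms are GP-linked.
2. Add to 9.7.2.2 a prespecified sensitivity analysis of all between-cohort comparisons, with both arms restricted to GP-linked patients and indication assigned from recorded diagnoses by the same rule.
3. List the difference in source population, and in how indication is assigned, among the limitations in 9.9.

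The full rivaroxaban cohort can stay in the main analysis of the hospital-based outcomes. The cost is protocol wording, an analysis-set flag and some extra analysis. Section 9.2 already defines the GP-linked subpopulation for the drug utilization analysis, so no new data source is needed. The GP-linked analysis will be less precise, as step 4 shows, and should be read for consistency with the main result, not as a separate test of the 1.5 margin.

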9.3 Variables

9.3.1 Patient characteristics and drug utilization

Descriptive variables of drug utilization will be presented only for the subpopulation captured by both the outpatient pharmacy database and the GP database, as only in this subpopulation sufficient information for the assignment of the indication of use is available. The following characteristics, including risk factors/potential confounders for the outcomes under study, will be presented for comparison between the two cohorts:

- age and sex distribution at index date 
- dose of index drug at index date (not available for vitamin K antagonists as dosing is determined in anticoagulation clinics) 

- dispensed amount (can be used to estimate duration of treatment) ✓
- where available based on hospital discharge diagnosis or from available GP notes, diagnosis associated with the prescribing of the index drug (where not available, dose and duration of index drug will be used as a proxy for the associated diagnosis among rivaroxaban users). Hospital discharge diagnoses and procedures will be identified within 4 weeks before until 7 days after the index date and GP diagnosed will be identified during the index month or in the month before the index date.
- proportion of patients defined as naïve, non-naïve, recent switchers and distant switchers ✓
- number of pregnant women at index date (if communicated by midwife or gynaecologist) ✓
- number of pregnancies after index date (if communicated by midwife or gynaecologist) ✓
- type of other anticoagulant use before the index date among the non-naïve group ✓
- use of specific prescribed medications both in the year before the index date and following the index date, confirming the ACS indication: antiplatelet drugs (low-dose acetylsalicylic acid, clopidogrel, dipyridamole, prasugrel, ticlopidine and ticagrelor); ✓
- use of other medications both in the year before the index date and following the index date: anticoagulants (including dabigatran etexilate and apixaban), antiarrhythmic drugs, antihypertensive drugs, statins, anti-diabetic agents, non-steroidal anti-inflammatory drugs, oral corticosteroids, acid-suppressive drugs, disease-modifying anti-rheumatic drugs, antidepressants, antipsychotic drugs, oral contraceptives, hormone-replacement therapy, strong inhibitors of either cytochrome P450 3A4 or P-glycoprotein (e.g. the systemic azole antimycotics ketoconazole, itraconazole, voriconazole and posaconazole and the HIV-protease inhibitor ritonavir), strong CYP3A4 inducers (e.g. rifampicin, phenytoin, carbamazepine or phenobarbital) and fluconazole. ✓
- renal status (estimated glomerular filtration rate [eGFR] or creatinine clearance [CrCl] to be obtained where available, and time of measurement relative to index date). Renal status to be defined as: normal renal function (CrCl > 80 mL/min); mild (CrCl < 80–50 mL/min), moderate (CrCl < 50–30 mL/min) or severe (CrCl < 30 mL/min) renal impairment and end-stage renal disease (CrCl < 15 mL/min) or requirement for dialysis). ✓
- smoking status and body mass index (BMI) recorded in the year before the index date and following the index date.
- hospital admissions for bleeding (see ICD-9 codes in Annex 3) in the year before the index date.
- healthcare utilization (e.g. hospital admissions) in the year prior to the index date. ✓

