- The prevention of venous thromboembolism (VTE) in adult patients undergoing elective hip or knee replacement surgery (recommended dose: 10 mg rivaroxaban od for 35 days following hip replacement surgery and 14 days following knee replacement surgery).
- Co-administered with acetylsalicylic acid (ASA) alone or with ASA plus clopidogrel or ticlopidine, for the prevention of atherothrombotic events in adult patients after an acute coronary syndrome (ACS) with elevated cardiac biomarkers (recommended dose 2.5 mg bid).

As is the case with other anticoagulants, clinical studies of rivaroxaban have identified haemorrhage as an important safety outcome ([Lassen et al. 2008](#); [Turpie et al. 2009](#)). A post-authorization safety study programme is planned for several European countries. The aim of this document is to summarize the design of a population-based study to characterise new users of rivaroxaban, assess patterns of drug utilization, including adherence to label recommendations, and to assess the risk of bleeding associated with rivaroxaban treatment in comparison with treatment with standard of care, in routine clinical practice in the Netherlands, for DVT/PE treatment, SPAF and ACS. For DVT/PE treatment and SPAF, standard of care is treatment with a vitamin K antagonist (acenocoumarol or phenprocoumon), and for the secondary prevention of ACS, standard of care is antiplatelet drug(s) such as low-dose acetylsalicylic acid, clopidogrel, dipyridamole, prasugrel, ticlopidine and ticagrelor. The standard of care treatments for ACS will require at least dual antiplatelet and be analysed as combination treatment, irrespective of the individual drug combinations used.

8 Research questions and objectives

This post-authorization study was designed to assess patient characteristics and patterns of drug utilization and to quantify outcomes related to safety and effectiveness in new users of rivaroxaban compared with new users of standard of care.

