9.1 Study design

This study has a cohort design.

Cohorts of first-time users of either rivaroxaban or standard of care will be identified using the date of first dispensing (index date) of the respective drug (index drug).

A patient will be considered eligible to enter the study cohort as a first-time user of rivaroxaban or a first-time user of “standard of care” when he or she has a first dispensing of the drug recorded during the enrolment period. In the Netherlands, for VTE prevention, DVT/PE treatment and SPAF, standard of care is treatment with a vitamin K antagonist (acenocoumarol or phenprocoumon), and for the secondary prevention of ACS, standard of care is antiplatelet drug(s) such as low-dose acetylsalicylic acid, clopidogrel, dipyridamole, prasugrel, ticlopidine and ticagrelor.

Patients who qualify as members of both cohorts on the same day, will be excluded. First-time users who have any record of being prescribed the other study drug prior to the enrolment period can only join their index drug cohort; these will be categorized as non-naïve, see below (i.e. patients with a previous dispensing of rivaroxaban can only join the standard of care cohort and those with a past dispensing for standard of care can only join the rivaroxaban cohort).

Patients who are first-time users of both rivaroxaban and comparison study drugs during the enrolment period will be assigned to a cohort based on first dispensing, with the date of this dispensing being the index date.

Many patients with ACS have a history of ischaemic heart disease for which platelet inhibition is standard treatment, and thus exclusion of patients with prior use of platelet inhibitors risks excluding a majority of typical ACS patients. Therefore, in patients treated for ACS, those who have been using a vitamin K antagonist or another oral anticoagulant-before the index date will be excluded but those who have been using one or more platelet inhibitors will remain eligible to enter the study.

Standard of care for ACS patients is combination therapy, and as such cohort assignment will be based on first use of rivaroxaban (in combination with aspirin or clopidogrel, or multi-antiplatelet therapy), or use of aspirin and clopidogrel and/or other antiplatelet medications.

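### ACS cohort membership can rest on antiplatelet dispensings after the index date, while follow-up starts at the index date

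*Protocol*

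**What the plan says.** Four parts of the protocol bear on this.

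- **Confirmation of the indication (9.3.1).** One listed variable is "use of specific prescribed medications both in the year before the index date and following the index date, confirming the ACS indication: antiplatelet drugs". It covers the year before the index date and an open-ended period after it. The list is introduced as characteristics that "will be presented for comparison between the two cohorts".
- **Combination requirement (7 and 9.1).** Section 7 states: "The standard of care treatments for ACS will require at least dual antiplatelet and be analysed as combination treatment". Section 9.1 says that "cohort assignment will be based on first use of rivaroxaban (in combination with aspirin or clopidogrel, or multi-antiplatelet therapy"), or on use of aspirin and clopidogrel and/or other antiplatelets. Neither section says when the second drug must be dispensed.
- **Index date (9.1).** Cohorts "will be identified using the date of first dispensing (index date) of the respective drug (index drug"). For ACS, earlier platelet-inhibitor users stay eligible. No rule says which dispensing sets the index date when the qualifying treatment is a combination.
- **Start of follow-up (9.7.2).** The cohorts "will be followed up from the index date until 12 months after the end of the enrolment period for potential outcomes". Crude incidence rates for all outcomes are planned for ACS as well as for the other two indications, and indication is a possible adjustment variable in the rate-ratio models.

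**The concern.** Suppose a patient has a first qualifying dispensing on day 0 and is accepted as an ACS patient because of an antiplatelet dispensing on day 30. That patient had to be alive and under observation on day 30. If days 0 to 30 still count as time at risk, the denominator holds time in which death or loss could not have occurred in anyone accepted this way. Patients who died early are missing from the numerator.

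For a non-fatal bleed the mechanism differs. The patient survives and may still be confirmed, so the time is not immortal. But a bleed that stops antiplatelet treatment may prevent confirmation, so membership is selected on what happens after the index date.

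Both mechanisms lower the ACS rates. A comparison is distorted when they act differently in the two cohorts, and the protocol leaves room for that. Under 9.3.1, dose and duration stand in for a missing diagnosis only among rivaroxaban users, whereas the ACS comparator must show at least two antiplatelets.

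**Working it through.** **Does the text allow it?**

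1. The variable that follows in 9.3.1, on other medications, uses the same before-and-after period but has no confirming role. Only the antiplatelet item has one.
2. The diagnosis windows in the same list are bounded: hospital diagnoses run from 4 weeks before to 7 days after the index date, and GP diagnoses cover the index month and the month before. The antiplatelet item has no upper bound.
3. The combination rule opens the same gap without 9.3.1. If the first antiplatelet dispensing is the index date and the second comes later, membership depends on reaching the second.
4. No section removes a patient who lacks a post-index antiplatelet dispensing. The text therefore permits the bias but does not require it.

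**How large could it be?** The protocol gives no lag, no share of patients qualifying at index and no ACS event rate. The inputs below are assumptions:

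- follow-up F = 365 days;
- constant hazard of a terminal event (death, or an event that ends dispensing);
- exponential lag to confirmation with mean L = 7, 30 or 90 days;
- a share q = 0, 0.5 or 0.9 already qualifying at index;
- patients never confirmed within F are dropped.

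For a low event rate, observed/true rate ≈ 1 − m/F, where m is the mean lag among those kept.

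With q = 0, m = L − F·e^(−F/L)/(1 − e^(−F/L)):

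- L = 7: m = 7.0, ratio 1 − 7.0/365 = 0.98
- L = 30: m = 30.0, ratio 1 − 30.0/365 = 0.92
- L = 90: e^(−365/90) = 0.0173, so m = 90 − 365 × 0.0173/0.9827 = 83.6, ratio 1 − 83.6/365 = 0.77

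With q > 0, m is multiplied by (1 − q)p/[q + (1 − q)p], where p = 1 − e^(−F/L). For L = 90 and q = 0.5: 83.6 × 0.491/0.991 = 41.4, ratio 0.89. For L = 90 and q = 0.9: 83.6 × 0.0983/0.9983 = 8.2, ratio 0.98.

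| Mean lag | none qualify at index | half qualify | 90% qualify |
|---|---|---|---|
| 7 days | 0.98 | 0.99 | 1.00 |
| 30 days | 0.92 | 0.96 | 0.99 |
| 90 days | 0.77 | 0.89 | 0.98 |

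A simulation with terminal event rates of 0.02 and 0.10 per person-year agrees to within about 0.01. In its 90-day row it gave 0.77, 0.88 to 0.89, and 0.97 to 0.98. If post-index use is described but does not decide membership, every cell is 1.

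The horizon also matters. A 30-day lag is 30/365 = 8% of one year but 30/180 = 17% of 180 days.

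**The protocol's own size figure.** The 12,000 rivaroxaban patient-years in 9.5 do not depend on this point. They reproduce with two-sided 0.05 (assumed): (1.960 + 0.842)² × 1.25/(ln 1.5)²/0.005 ≈ 11,936. Nothing in the fix changes them.

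**The case against.** The best defence is that the antiplatelet item is descriptive. It sits among variables presented for the drug utilization analysis, in the GP-linked subpopulation only, and it counts use before the index date too. Indication is assigned by other means: diagnoses near the index date, and dose and duration where these are missing. For the outcome analysis, 9.2 and 9.4 name dosing as the proxy and do not mention antiplatelet confirmation. Section 9.1 can also be read as requiring the combination to be present at first use, so that entry and index date coincide. Since prior antiplatelet users stay eligible, many patients may qualify at index. The exact window could be left to an analysis plan.

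Much of this stands, and it limits both the certainty and the size. It does not settle the matter. The same list holds the rules for assigning indication, so it is not purely descriptive, and the item is explicitly given a confirming role. The dosing proxy does nothing for comparator patients. The index date and the start of follow-up are fixed in this protocol, so the order of qualification and follow-up is a protocol matter.

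A reader might infer more: that immortal time is certainly built into the ACS cohorts, or that a true ACS rate ratio of 1 would appear as 0.92 (335/365), or as 0.79 (335/425) with a threefold hazard in the first 30 days. The documents do not support this. Those ratios need a fixed 30-day delay for every patient, nobody qualifying at index, and the whole delay in one cohort only. They also treat every event as impossible before confirmation, although the primary outcomes are hospitalized bleeds that patients can survive. Section 9.7.2 does not specify a separate ACS rate ratio either.

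**Conclusion.** The point holds as a conditional one. As written, the protocol allows ACS membership to rest on information from after the start of follow-up, with no time limit. If it is applied that way, the ACS incidence rates and any ACS comparison can be biased. Immortal time arises for death and loss, and selection on the future for bleeds that end antiplatelet treatment.

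The table gives the assumed range for a terminal event within one cohort. It shows a negligible effect if most patients qualify at index and a material one if few do and lags are long. The direction and size of any effect on a rate ratio depend on how the lag differs between cohorts, which the document does not give. Equal lags would largely cancel. The other indications are not touched by this point. It is worth correcting before analysis, because the change is small and the ambiguity affects who is counted.

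**What to change.** In 9.1 and 9.3.1, state that ACS membership is determined from diagnoses and antiplatelet dispensings up to and including the index date, and that for ACS the index date is the dispensing that completes the qualifying combination. Apply this in the same way to both cohorts.

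If a short confirmation window after the index date is kept, state its length and start follow-up at its end for all ACS patients in both cohorts, including those who qualified earlier. The existing hospital-diagnosis window, which runs to 7 days after the index date, needs the same treatment for ACS.

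Report antiplatelet use after that point as a descriptive variable only, and remove its confirming role from 9.3.1.

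The cost is wording in two sections, plus a matching line in 9.7.2 if the window option is chosen. Some ACS patients will enter slightly later or will not be confirmed. The stated study size does not change.
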